Randomization and the first dose of belimumab should be completed within 35 days of initiation of screening procedures. Participants will be receiving stable standard therapy at entry. At randomization, participants will be stratified by their screening SLEDAI-2K score (≤9 vs. ≥10), by immunosuppressant use at screening (immunosuppressant use vs. no use) and by screening corticosteroid dose (prednisone equivalent ≤10 mg/day vs. >10 mg/day). Belimumab will be administered SC on Day 1 and then weekly (i.e., every 7 days ±1 day) through Week 51 for Arms A and B, and through Week 103 for Arm C. SC injections will be administered at alternating injection sites between the left or right thighs and the abdomen. Rituximab-placebo or rituximab will be administered by intravenous (IV) infusions at Weeks 4 and 6 for Arms A and B. Participants in Arms A and B will be administered a pre-medication regimen 30 minutes before each rituximab-placebo or rituximab infusion on Weeks 4 and 6, including methylprednisolone 100 mg IV or equivalent, an antihistamine, and acetaminophen or equivalent.

Participants in any arm who are deemed treatment failures for efficacy endpoints at any time during the study will be encouraged to remain in the study and continue to have all efficacy and safety assessments.

Participants randomized to Arms A or B who enter the study on immunosuppressants will discontinue immunosuppressants prior to or on the day of the Week 4 visit. Continuing the stable immunosuppressant dose until Week 4 allows participants to receive 3 weeks of belimumab SC prior to discontinuing their immunosuppressants. Corticosteroids may be adjusted as necessary during this transition period. If participants in Arms A and B receive immunosuppressants after the Week 4 visit they will be deemed treatment failures. Participants in Arm C will continue their stable immunosuppressants throughout the study at the discretion of the investigator. If participants in Arm C require an increased dose of their stable immunosuppressant after Week 12 or addition of a new immunosuppressant they will be considered a treatment failure.

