7.3. Method of Treatment Assignment

All participants will be assigned to study treatment in accordance with the randomization schedule and randomization must occur before any investigational product is administered. Participants will be centrally randomized using an Interactive Web Response System (IWRS). Before the study is initiated, the log in information and directions for the IWRS will be provided to each site. A participant will be assigned a subject number at the time the informed consent is signed. Once a subject number has been assigned to a participant, it cannot be re-assigned to another participant.

A randomization schedule will be generated with the following treatment assignments:

Arm	Treatment Description
А	Belimumab SC for 52 weeks + Rituximab IV Placebo at Weeks 4 and 6
В	Belimumab SC for 52 weeks + Rituximab IV 1000 mg at Weeks 4 and 6
С	Belimumab SC plus standard therapy for 104 weeks

Study treatment will be dispensed at the study visits summarized in the SoA (Section 2). Returned study treatment should not be re-dispensed to the participants. In the event that a subject is unable to attend their planned study visit (see Section 2) to receive their carton of belimumab autoinjectors, if allowable under local regulations and approved by the sponsor, the investigator may with the agreement of the subject arrange to have the autoinjectors dispensed and shipped directly to the subject.

At least 280 participants will be randomized in a 1:2:1 ratio to 1 of 3 treatment groups: belimumab plus rituximab-placebo (Arm A, target N=70), belimumab plus rituximab (Arm B, target N=140), or belimumab plus standard therapy (Arm C, target N=70). Randomization of participants will be stratified by screening SLEDAI-2K score (\leq 9 vs. \geq 10), immunosuppressant use at screening (immunosuppressant use vs. no use), and screening corticosteroid dose (prednisone equivalent \leq 10 mg/day vs. \geq 10 mg/day).

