10.4.2. Safety Analyses

All safety analyses will be performed on the ITT Population.

Endpoint	Statistical Analysis Methods
Secondary	Descriptive statistics will be used to summarize AEs, SAEs, AEs of special interest (AESI), changes in laboratory parameters, and immunogenicity (both antibelimumab and anti-rituximab antibodies will be assessed). The frequency of laboratory abnormalities will be tabulated by treatment group. The frequency of AEs will be tabulated by MedDRA system organ class (SOC) and preferred term and compared between treatment arms.

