| 23.13. | 23.11 | ITT | Adverse Events by SOC and PT and Race - On Study (Year 1&2) | 
 Now presents data for Year 1&2 |
| 23.14. | 23.13 | ITT | Adverse Events by SOC and PT and Baseline C3/C4 Levels and Anti-dsDNA – On Study (Year 1&2) | 
 Now presents data for Year 1&2 |
| 23.15. | 23.22 | ITT | Adverse Events Leading to Permanent Discontinuation of Study Treatment by SOC and PT – Belimumab – On Study (Year 1&2) | 
 Now presents data for Year 1&2 |
| 23.16. | 23.23 | ITT | Common [1] Non-Serious Adverse Events by SOC and PT - On Study (Year 1&2) | 
 Now presents data for Year 1&2 |
| Deaths and Serious Adverse Events | | | | |
| 23.17. | 23.18 | ITT | Death by Category and PT - On Study (Year 1&2) | 
 Now presents data for Year 1&2 |
| 23.18. | 23.19 | ITT Year 2 | Serious Adverse Events by SOC and PT - On Study (Year 2) | 
 Use new 'ITT Year 2' Population defined in Section 2.2. |
| 23.19. | 23.20 | ITT | Serious Adverse Events by SOC and PT - On Study (Year 1&2) | |
| 23.20. | 23.24 | ITT | Study Treatment Related Serious Adverse Events by SOC and PT - Belimumab Only [1] - On Study (Year 1&2) | 
 Now presents data for Year 1&2 |

| Safety Tables | | | | |
|---|-------------------|------------|--|---|
| New output number | Old output number | Population | Title | Major modifications since original RAP |
| 23.21. | 23.25 | ITT | Study Treatment Related Serious Adverse Events by SOC and PT - Rituximab Only [1] - On Study (Year 1&2) | 
 Now presents data for Year 1&2 |
| 23.22. | 23.26 | ITT | Study Treatment Related Serious Adverse Events by SOC and PT – Both Belimumab and Rituximab [1] - On Study (Year 1&2) | 
 Now presents data for Year 1&2 |
| 23.23. | NEW | ITT | Study Treatment Related Serious Fatal and Non-Fatal Adverse Events by PT – Belimumab Only [1] - On Study (Year 1&2) | 
 New output (required for Plain Language Summary) |
| 23.24. | NEW | ITT | Study Treatment Related Serious Fatal and Non-Fatal Adverse Events by PT - Rituximab Only [1] - On Study (Year 1&2) | 
 New output (required for Plain Language Summary) |

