| 23.25. | NEW | ITT | Study Treatment Related Serious Fatal and Non-Fatal Adverse Events by PT – Both Belimumab and Rituximab [1] - On Study (Year 1&2) | 
 New output (required for Plain Language Summary) |
| Survival Status | | | | |
| 23.26. | 23.29 | ITT | Survival Status at Week 104 | |
| Adverse Events of Special Interest (AESI) | | | | |
| 23.27. | 23.30 | ITT Year 2 | Adverse Events of Special Interest by Category - On Study (Year 2) | 
 Use new 'ITT Year 2' Population defined in Section 2.2. |
| 23.28. | NEW | ITT | Adverse Events of Special Interest by Category - On Study (Year 1&2) | 
 New output (omission in original RAP) |
| 23.29. | 23.31 | ITT | Malignant Neoplasm Adverse Events of Special Interest by Category and PT - On Study (Year 1&2) | 
 Now presents data for Year 1&2 |
| 23.30. | 23.32 | ITT | Post Belimumab SC Injection Systemic Reactions Adverse Events of Special Interest by Category and PT - On Study (Year 1&2) | 
 Now presents data for Year 1&2 |
| 23.31. | 23.33 | ITT | Serious Post Belimumab SC Injection Systemic Reactions Adverse Events of Special Interest by Category and PT - On Study (Year 1&2) | 
 Now presents data for Year 1&2 |

| Safety Tables | | | | |
|---|-------------------|------------|---|--|
| New output number | Old output number | Population | Title | Major modifications since original RAP |
| 23.32. | 23.34 | ITT | Infection Adverse Events of Special Interest by Category and PT - On Study (Year 1&2) | 
 • Now presents data for Year 1&2 |
| 23.33. | 23.35 | ITT | Infection Adverse Events of Special Interest Leading to Belimumab SC Study Treatment Discontinuation by Category and PT - On Study (Year 1&2) | 
 • Now presents data for Year 1&2 |
| 23.34. | 23.36 | ITT | Depression/Suicide/Self-injury Adverse Events of Special Interest by Category and PT - On Study (Year 1&2) | 
 • Now presents data for Year 1&2 |
| 23.35. | 23.41 | ITT | Adverse Events of Special Interest including Exposure-Adjusted Incidence Rates by Category – On Study (Year 1&2) | 
 • Now presents data for Year 1&2 |
| COVID-19 Pandemic Adverse Events | | | | |

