6.6. Time to Study Treatment Discontinuation

This only includes the belimumab study medication as prescribed in Year 1 (and Year 2 for Arms C) i.e. this does not include re-start belimumab for subjects in Arms A&B in Year 2.

Year 1 (all arms) and Year 1&2 for Arms A&B only

- If the last dose of belimumab+10 days is prior to the Week 52 visit date (where Week 52 visit date is as observed, or predicted as day1+364 for subjects who do not have a Week 52 visit) then the subject has discontinued treatment (had the event / CENSOR=NO=0) at the earliest non-missing date of (last dose date +7, date of death, withdrawal date, LTFU date)
- If the last dose of belimumab + 10 days is on or post the Week 52 visit date (where Week 52 visit date is as observed, or predicted as day1+364 for subjects who do not have a Week 52 visit) then the subject has a censored time to discontinued treatment (does not have the event / CENSOR=Yes=1) at the earliest non-missing date of (observed or predicted Week 52 visit date, death date, withdrawal date, LTFU date)

Year 1&2 for arm C only

- If the last dose of belimumab + 10 days is prior to the Week 104 visit date (where Week 104 visit date is as observed, or predicted as day1+728 for subjects who do not have a Week 104 visit) then the subject has discontinued treatment (had the event / CENSOR=NO=0) at the earliest non-missing date of (last dose date +7, date of death, withdrawal date, LTFU date)
- If the last dose of belimumab + 10 days is on or post the Week 104 visit date (where Week 104 visit date is as observed, or predicted as day1+728 for subjects who do not have a Week 104 visit) then the subject has a censored time to discontinued treatment (does not have the event / CENSOR=Yes=1) at the earliest non-missing date of (observed or predicted Week 104 visit date, death date, withdrawal date, LTFU date)

A KM plot of time to belimumab treatment discontinuation will also be generated [F11.02]. The figures will be repeated for the Week 104 reporting with all data from Year 1 and 2 combined [F21.02]. Due to the design of the study Arms A & B will be truncated at the end of Year 1. A listing of subjects who discontinued belimumab or Rituximab treatment, including reason will be produced [L11.04, L11.05 , L21.03].

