- A summary of Adverse Events leading to Permanent Discontinuation of Belimumab Study Drug including Exposure-Adjusted Incidence Rates will be produced for Year 1 On Treatment (Section 5.12) [T13.45] and Years 1&2 combined On Study (Section 5.11) [T23.39]. These will present Adverse Events Overall and by System Organ Class and Preferred Term and will display:
 - the number of subjects experiencing the event (n);
 - For Year 1: the sum of the total time to the first event or total on treatment time* if no event (years) across all subjects (e), * defined in Section 15.6.2: On Treatment Exposure (Year 1);
 - For Years 1&2 combined: the sum of the total time to the first event or total on-study time* if no event (years) across all subjects (e), * defined in Section 15.6.2: On-Study Exposure (Years 1&2 Combined);
 - the exposure adjusted subject rate per 100 subject years ($r = (n/e)*100$).

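### Final-report Tables 23.15 and 23.33 compare adverse events leading to belimumab discontinuation over about 51 weeks of planned dosing in Arms A/B and about 103 weeks in Arm C

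*SAP*

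**What the plan says.** **Dosing.** The protocol synopsis gives weekly belimumab "through Week 51 for Arms A and B, and through Week 103 for Arm C". The treatment table in protocol Section 7.3 describes the same plan as "Belimumab SC for 52 weeks + Rituximab IV 1000 mg at Weeks 4 and 6" for Arm B (Arm A has the same belimumab course) and "Belimumab SC plus standard therapy for 104 weeks" for Arm C. RAP Section 5.12 defines no on-treatment period for Arms A and B in Year 2, because they are then off treatment.

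**Tables.** Section 2.1.7 of the second RAP addendum lists Table 23.15, "Adverse Events Leading to Permanent Discontinuation of Study Treatment by SOC and PT – Belimumab – On Study (Year 1&2", and Table 23.33, "Infection Adverse Events of Special Interest Leading to Belimumab SC Study Treatment Discontinuation by Category and PT - On Study (Year 1&2". Both use the ITT population, and both are marked as now presenting Years 1 and 2 together. RAP Section 5.11 runs that on-study window from first belimumab dose to study completion or withdrawal, in every arm. RAP Section 8.1.2 fixes the content of such tables: number and percentage of subjects, and number of events.

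**Same event elsewhere.** For the Kaplan-Meier plot of time to belimumab discontinuation, RAP Section 6.6 leaves out re-start belimumab and states: "Due to the design of the study Arms A & B will be truncated at the end of Year 1". No such rule is written for the adverse-event tables.

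**Use.** Protocol Section 10.4.2 makes the safety analysis descriptive, then says: "The frequency of AEs will be tabulated by MedDRA system organ class (SOC) and preferred term and compared between treatment arms".

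**The concern.** An adverse event can lead to discontinuation of study belimumab only while study belimumab is being given. In Arms A and B that is roughly the first half of the window these tables cover. In Arm C it is nearly all of it. A reader who compares the columns sees a higher percentage in Arm C that comes partly or wholly from the planned length of dosing.

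Arm C is in the trial as a qualitative reference against which to judge the other two arms. Serious infection is a risk that the protocol singles out for co-administration. A display that makes the combination look better tolerated than belimumab plus standard therapy, infections included, because its course is shorter would mislead on a point that readers will look for. The report would also treat one event in two ways: truncated for Arms A and B in the plot, and not in the tables.

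**Working it through.** **1. Reproduce the stated course lengths.** The RAP exposure formula (Section 6.5) is last injection date − first injection date + 7 days. A last dose at Week 51 gives 51 × 7 + 7 = 364 days = 52 weeks. A last dose at Week 103 gives 103 × 7 + 7 = 728 days = 104 weeks. These match the 52 and 104 weeks in protocol Section 7.3.

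**2. Ratio of time at risk.** 103/51 = 2.02, or 104/52 = 2.00 by the exposure formula.

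**3. Percentage of subjects with an event, at equal true rates.** The documents give no discontinuation rate, so q and d are assumed. Let q be the annual risk of an event that stops belimumab and d the yearly dropout from other causes. Weekly hazards are λ = −ln(1 − q)/52 and μ = −ln(1 − d)/52. The expected proportion over T weeks is

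P(T) = λ/(λ + μ) × [1 − exp(−(λ + μ)T)], with T = 51 for A/B and T = 103 for C.

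Example with q = 5%, d = 0: λ = 0.000986; P(51) = 1 − exp(−0.0503) = 4.91%; P(103) = 1 − exp(−0.1016) = 9.66%; ratio 1.97.

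| q | d | Arms A/B | Arm C | C ÷ A/B |
|---|---|---|---|---|
| 5% | 0 | 4.91% | 9.66% | 1.97 |
| 5% | 10% | 4.66% | 8.73% | 1.87 |
| 5% | 15% | 4.54% | 8.28% | 1.83 |
| 10% | 0 | 9.82% | 18.84% | 1.92 |
| 10% | 10% | 9.34% | 17.06% | 1.83 |
| 10% | 15% | 9.09% | 16.19% | 1.78 |

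Ratios use unrounded values. A fair display would give 1.00 in every row.

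**4. Falling hazard.** Take a first-year risk of 8% and halve the hazard after Week 51. With no dropout the result is 7.85% against 11.62%, ratio 1.48. With 15% yearly dropout it is 7.27% against 10.23%, ratio 1.41.

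**5. Raw counts.** At q = 5%, d = 0 and the target sizes 70/140/70: Arm A 70 × 0.0491 = 3.4, Arm B 140 × 0.0491 = 6.9, Arm C 70 × 0.0966 = 6.8 subjects.

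**6. Re-start belimumab.** If events stopping re-start belimumab in Arms A/B were counted, and 30% re-started for a mean of 26 weeks (assumed), the time ratio would be 103/(51 + 0.3 × 26) = 103/58.8 = 1.75.

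**7. Does the remedy work?** Restricting Arm C to the first year gives a ratio of 1.00. Dividing by time actually on belimumab also gives 1.00 (5.13 per 100 patient-years in both groups at q = 5%). RAP Section 5.12 adds 28 days after the last dose, so its denominators would be about 55 and 107 weeks. Their ratio is 107/55 = 1.95, and 2.02/1.95 leaves a residual of about 1.04, which is small.

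**The case against.** The strongest reply is that an equal-window comparison is already planned. The first report has Year 1 tables of adverse events leading to discontinuation (T13.26, T13.27), infection events leading to discontinuation (T13.42), and a Year 1 exposure-adjusted discontinuation table on on-treatment time (T13.45). The final report keeps the truncated plot, the belimumab exposure table (21.10) and a Year 2 listing of events that stopped belimumab (Listing 23.03). Arm C is open-label, has different concomitant-medication rules and is not tested against the other arms. Cumulative incidence over a one-year and a two-year regimen is also a legitimate description of those regimens. All of this stands. It lowers the consequence, but it does not make the columns of the two final-report tables comparable.

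Other limits also stand:

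- The RAP does not say whether an event that stops re-start belimumab in Year 2 enters these tables. The titles and Section 6.6 suggest not, but Section 6.6 is written for time to discontinuation only. A reader might infer that no Arm A/B event can appear in Year 2. The documents do not settle that.
- The table shells are separate documents, so an explanatory footnote cannot be ruled out.
- The discontinuation row of summary Table 23.02 concerns study treatment in general, which in Arms A/B includes rituximab or its placebo. The belimumab ratios do not carry over to it.

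**Conclusion.** The point holds for Tables 23.15 and 23.33 in the final report, as a fault of display in a descriptive comparison with Arm C. With equal true rates, the Arm C percentage would be about 1.8 to 2.0 times that of Arms A/B under a constant hazard, annual risk 5–10% and yearly dropout 0–15%. It would be about 1.4 to 1.5 times if the Year 2 hazard is half that of Year 1. All of these rates are assumed.

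Three stronger readings are tempting, and the documents do not support them:

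- *Arm C will show twice the events.* This concerns percentages only. Against Arm B, which is twice the size, the raw counts would be about the same (6.9 and 6.8 in the example). A full doubling also needs a steady hazard and little dropout.
- *The main safety comparison is distorted.* Arms A and B have the same planned belimumab period, so B against A is unaffected.
- *The trial has no fair comparison with Arm C on this outcome.* The Year 1 outputs provide one.

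**What to change.** Present Tables 23.15 and 23.33 in two blocks, in line with the truncation in RAP Section 6.6:

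1. Day 1 to the Week 52 visit, Arms A, B and C. This is the only between-arm comparison.
2. After the Week 52 visit, Arm C only. An Arm C event that starts before the visit but stops belimumab after it belongs here, since its counterpart in Arms A/B could not have counted.

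Footnote the planned dosing lengths. State that events stopping re-start belimumab in Arms A/B are not counted, or list them separately. Cross-refer to the Year 1 tables. If a rate is added, divide by belimumab on-treatment time (RAP Section 5.12). The original RAP's "A summary of Adverse Events leading to Permanent Discontinuation of Belimumab Study Drug including Exposure-Adjusted Incidence Rates" (T23.39 for Years 1 and 2) is not on the abridged list and need not be restored for this purpose, because its two-year denominator is on-study time. For the discontinuation row of Table 23.02, use the same split or a footnote.

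The cost is a change to table shells and programs on data already collected. Each table gains one block, and the first block will largely repeat existing Year 1 output.

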2.1.8. Safety Figures

There are no Safety Figures to produce.

2.1.9. Safety Listings

| Safety Listings | | | | |
|-----------------------|-------------------|------------|---|--|
| New output number | Old output number | Population | Title | Major modifications since original RAP |
| Adverse Events | | | | |
| 23.01. | 23.02 | ITT | Adverse Events (Year 2) | |
| 23.02. | 23.03 | ITT | Adverse Events Related to Belimumab SC (Year 2) | |
| 23.03. | 23.05 | ITT | Adverse Events Resulting in Belimumab SC Study Treatment Discontinuation (Year 2) | |
| 23.04. | 23.07 | ITT | Year 1 Adverse Events reported after LSLV (Year 1) | |
| 23.05. | 23.08 | ITT | Serious Adverse Events (Year 2) | |

| Safety Listings | | | | |
|---------------------------|--------------------------|-------------------|---|---|
| New output number | Old output number | Population | Title | Major modifications since original RAP |
| 23.06. | 23.11 | ITT | Reasons for Considering as a Serious Adverse Event (Year 2) | |
| 23.07. | 23.13 | ITT | MedDRA coding changes (Year 2) | |
| Laboratory Results | | | | |
| 23.08. | 23.14 | ITT | Laboratory Results: Hematology (Year 2) | |
| 23.09. | 23.15 | ITT | Laboratory Results: Liver Function (Year 2) | |
| 23.10. | 23.16 | ITT | Laboratory Results: Electrolytes (Year 2) | |
| 23.11. | 23.17 | ITT | Laboratory Results: Other Chemistries (Year 2) | |
| 23.12. | 23.18 | ITT | Laboratory Results: Urinalysis (Year 2) | |
| 23.13. | 23.19 | ITT | Laboratory Results: Immunoglobulins (Year 2) | |
| Immunogenicity | | | | |
| 23.14. | 23.26 | ITT | Immunogenicity Results for Belimumab SC (Year 2) | |
| COVID-19 Pandemic | | | | |
| 23.15. | 23.27 | ITT | COVID-19 Assessments and Symptom Assessments for Subjects with COVID-19 Adverse Events (Year 1&2) | |

2.1.10. Health Outcomes Tables

| Health Outcomes Tables | | | | |
|------------------------|-------------------|------------|---|--|
| New output number | Old output number | Population | Title | Major modifications since original RAP |
| Health Outcome Tables | | | | |
| 24.01. | 24.01 | MITT | Patient Global Assessment of Disease Activity Change from Baseline by Visit (Hypothetical) (Year 1&2) | |
| 24.02. | 24.02 | MITT | Lupus Quality of Life Domain Scores Change from Baseline by Visit (Hypothetical) (Year 1&2) | |
| 24.03. | 24.03 | MITT | FACIT-Fatigue Scale Score Change from Baseline by Visit (Hypothetical) (Year 1&2) | |
| 24.04. | 24.04 | MITT | Improvement in FACIT-Fatigue Scale Score exceeding the MCID (>=4 point increase) by Visit (Hypothetical) (Year 1&2) | |
| 24.05. | 24.05 | MITT | WPAI: Overall Work Productivity Impairment Change from Baseline by Visit (Hypothetical) (Year 1&2) | |
| 24.06. | 24.06 | MITT | WPAI: Percent Activity Impairment Score Change from Baseline by Visit (Hypothetical) (Year 1&2) | |

2.1.11. Health Outcomes Figures

| Health Outcomes Figures | | | | |
|-------------------------|-------------------|------------|---|--|
| New output number | Old output number | Population | Title | Major modifications since original RAP |
| Health Outcome Figures | | | | |
| 24.01. | 24.02 | MITT | Lupus Quality of Life Domain Scores Change from Baseline by Visit (Observed) (Year 1&2) | |

| Health Outcomes Figures | | | | |
|-------------------------|-------------------|------------|--|--|
| New output number | Old output number | Population | Title | Major modifications since original RAP |
| 24.02. | 24.03 | MITT | FACIT-Fatigue Scale Score Change from Baseline by Visit (Observed) (Year 1&2) | |
| 24.03. | 24.04 | MITT | Improvement in FACIT-Fatigue Scale Score Exceeding the MCID (>=4 points increase) by Visit (Observed) (Year 1&2) | |

